Feasibility and acceptability of a web-based physical activity for the heart (PATH) intervention designed to reduce the risk of heart disease among inactive African Americans

NCT04280783

Date: October 27, 2020

Protocols for the intervention and control groups.

After randomization, each participant in the intervention group will be given a password-protected profile to access the PATH website and a detailed orientation on how to use all the resources included in PATH (see Table 1). The control group will be introduced to *Be Active Your Way* booklet and newsletters which they will be encouraged to use for 12 weeks while awaiting the intervention.

The treatment group: The PATH group will be granted password protected access to one of the 3 PATH levels based on their baseline fitness status. The intervention is designed to help participants increase their baseline PA via health coaching, self-monitoring and pragmatic workout videos that provide convenient options for overcoming socio-environmental barriers to PA. After randomization, the PA coach will work with each participant to develop their PA prescription guided by the FITT-VP principle¹ which recommends the frequency, intensity, time/duration, type, volume and progression of PA regimen. The goal of the exercise prescription will be to increase baseline MVPA by ≥ 60 min/week or 6000 steps/week over the course of the study. Our PA prescription process will begin by identifying a suitable PATH level for each participant based on their estimated maximum rate of oxygen consumption during incremental exercise (VO₂ max).¹ The VO₂ max will be predicted using a validated non-exercise prediction model for peak VO₂ (VO₂ peak) whose covariates include sex, age, waist circumference, resting heart rate and PA index.² Individuals with predicted VO₂ max $\leq 35^{\text{th}}$ percentile rank for their age and gender will be assigned to the Beginner PATH level (includes light intensity PA <3 METs). Those with VO₂ max between 35th and 75th percentile rank will be assigned to Intermediate PATH level which includes moderate intensity PA (3-6 METs) in addition to the Beginner PATH content. Participants with VO₂ max greater than 75th percentile rank will be assigned to Proficient PATH level which includes vigorous intensity PA (>6 METs) in addition to the Intermediate PATH content. After assigning PATH level, the PA coach will guide each participant in selecting their weekly PA goal and will help them plan to start slow with a plan to establish regular exercise frequencies of 3-5 days every week. The coach will also guide participants to select activities with intensity that help them progress along the PA continuum (i.e., sedentary to light PA to MVPA). To foster safety, participants will be instructed to use the Borg Rating of Perceived Exertion (RPE) Scale³ as a guide for adjusting the intensity of their PA regimen. The scale ranges from 6 (no exertion at all) to 20 (maximal exertion) and is embedded with each workout video on PATH. Specifically, the participants will be asked to maintain PA at perceived exertion ratings between 12 to 14 (i.e., moderate level of intensity) on the RPE Scale. To ensure gradual progression in PA intensity, each participant's progress will be reviewed every 2 wks, and more intensity will be allowed, including transition to the next PATH level, when most workouts within the assigned PATH level are perceived to be "very light" (≤ 9 on the RPE Scale). Participants will be requested to rate each workout they engage in on the RPE scale. This method will ensure that the prescribed PA regimen for each individual is based on their physical ability and fitness status. Although the PA coach will provide solid examples of the combination of workout videos that could help participants attain their personalized goals, each participant will have access to all resources within their PATH level and will be encouraged to select a PA regimen that includes their preferred workout videos and other types of PA appropriate for their fitness. The workouts that are recommended by the PA coach and those selected by each participant as favorites will be featured on the personalized PATH dashboard. Box 1 illustrates a PA prescription for Mary, where in the first 2 wks her PA regimen includes her usual walks (40 mins of MVPA/wk or 4000 steps/week) and 10 mins of additional dance workouts each week.

Box 1. Mary's PA prescription

Mary is a 45-year old woman with a VO₂ max of 25.1 (5th percentile). She reports 40 mins of MVPA & 4000 steps derived from walking for 20 mins twice/week. Her preference is to ↑ her PA by using dance workout videos. The PA coach will assign Mary to Beginner PATH level based on her VO₂ max, and work with her to develop a plan to ↑ her MVPA by 60 mins/week or 6000 steps/week at the end of study:

- ✓ Gradually increase PA frequency (e.g., an additional day of PA every 4 wks)
- ✓ Set limits for PA intensity: start with workouts that she can do at perceived exertion ratings between 12 to 14. The progress will be reviewed every 2 wks, with more intensity allowed when most workouts within the assigned PATH level are perceived to be "very light" (9 on the RPE Scale).
- ✓ Gradually increase the time. The duration of her PA regimen can be increased by 10 mins of MVPA or 1000 steps every week for the first 6 wks, then maintain.
- ✓ Recommend workout videos with types of PA that align with her goals. The coach will recommend specific workouts that can help Mary attain her goals, but she will have an option to select her favorite workouts at any time.
- ✓ Flexible strategy for attaining desired PA volume. Mary can attain the desired volume of weekly PA by either ↑ her routine walks or via her favorite workouts.
- ✓ Evaluation of progress every 2wks. The PA coach will call Mary twice a month to review and revise the PA prescription based on the progress made. After 6 successful weeks, Mary can focus on maintaining her MVPA at 100 mins/wk or 10,000 steps/wk. She can also continue with the gradual increase in PA volume.

The PA prescription will be revised after every 2 weeks based on the progress made. Those who manage to increase PA by ≥ 10 minutes each week of MVPA or 1000 steps for 6 consecutive weeks will attain the study goal and their plan for the remaining study period will be to maintain the improved PA regimen. However, the participant can opt to continue with gradual increase in PA volume. To simplify access and support PA maintenance, the workout videos are organized in specific categories (e.g., walking, dance, steps aerobics) and can be sorted by duration and METs. To reduce risk of injury, the amount and intensity of PA will be increased gradually over the course of the study, as advocated by ACSM.⁴ Although there are no established standards on how to increase PA gradually, available evidence suggests that it is safe to increase

MVPA by about 10 minutes or 1000 steps every week.^{4,5} Each participant will be provided near real-time data on their progress towards their weekly and monthly goals on the PATH dashboard. *To complete the PA prescription, participants will provide their preferred schedule for receiving PA reminders and twice a month phone calls from the PA coach to monitor progress and revise PA goals.* Participants will also be given contacts of the PA coach with instructions to reach out if they need help before scheduled calls. During the study period, participants will be encouraged to adhere to their PA goals and share their experiences on the PATH community forum moderated by the study staff. At the end of the study, we will survey participants for feedback on resources that were most helpful to them and ideas for improving the PATH intervention.

Wait-list control group: Participants in this group will not have access to the PATH intervention until after 12 weeks when they cross over. After randomization, the control group will be provided with a copy of the *Be Active Your Way* booklet, developed by the Centers for Disease Control (CDC) to help individuals integrate PA in their daily lives.⁶ The key strategies used in the booklet are outlined in Box 2. We have chosen this control strategy to mirror usual care where patients are provided with self-help handouts. The *Be Active Your Way* booklet was selected because it is evidence based, free to download and recommended by the CDC as a pragmatic self-help resource for promoting PA.⁶ In addition, the control group will receive bi-weekly newsletters focusing on general health. The control group data will help contrast the important aspects of our study, including differential ActiGraph use and retention rates between the control and intervention groups, as well as the trend in PA and cardiometabolic risk changes. After 12 weeks, the outcome assessments will be done, and the control group will be given access to the PATH intervention. Once given access to PATH, participants will be subject to all the study procedures described for the treatment group. No follow-up is planned after the post-intervention assessments for both the intervention and control groups.

Box 2. Be Active Your Way get started plan

- ✓ **Goal:** Build up your PA routine overtime.
- ✓ **Start by doing what you can** & then look for ways to do more. If you have not been active for a while, start out slowly. After several wks or months, build up your activities, then do them longer & more often.
- ✓ **Walking is one way to add PA to your life.** When you first start, walk for 10 mins a day on a few days during the first couple of weeks.
- ✓ **Add more time and days.** Walk a little longer. Try 15 min instead of 10 mins. Then walk on more days/wk.
- ✓ **Pick up the pace.** Once this is easy to do, try walking faster. Keep up your brisk walking for a couple of months. You might add biking on weekends for variety.

Expected results, potential pitfalls and solutions: Although

a wait-list control design may artificially inflate the intervention effects in an efficacy trial,⁷ our feasibility study primary focus is on within-group changes. Therefore, a wait-list strategy may enhance retention and help control for passage of time and assessments⁸ without impacting study outcomes. Another potential pitfall is recruitment. However, based on our experiences, we do not anticipate significant difficulties recruiting women, but more proactive strategies will be needed to recruit men and minorities. To address the challenge, we have built relationships with strategic community stakeholders such as barbershops where men frequent, and the CTSI Community PARTners core which specializes on recruiting minorities. In addition, the remote nature of the intervention is likely to make the study appealing to men and other underserved populations with low participation in biomedical research. These strategies will help us attain our recruitment targets. To foster safety, our exclusion criteria will help exclude individuals who are unfit to engage in unsupervised PA. Moreover, the PA prescriptions will be personalized according to ability and preference. All participants will be educated on PA safety using ACSM Guidelines⁴ and will be given non-slip exercise mats.

Screening assessments – Questionnaires will be used to assess barriers to exercise self-efficacy, PA readiness, medical history and risk of diabetes, PA habits, sleep patterns, depressive symptomatology, diet, fatigue, and stress. Table 1 outlines the specific data collection instruments and their timeline. These data will be used to evaluate eligibility and to describe lifestyle and other cardiometabolic factors typically related to PA.

Measures of adherence and acceptability (Aim 1). Wrist-worn ActiGraph GT9X will be used to measure PA outcomes. Throughout the 12-week Study, participants will be asked to self-monitor their daily PA. The PA tracker will be worn on the wrist for at least 10 hours per day when a participant is awake. The tracker will be connected to the CenterPoint app which will help the study team monitor the participants' progress throughout the study. Two weeks and one week before the end of the study, the study team will send reminders to participants (via text message, email, phone call and push notification) to wear their PA tracker for 7 days before they are scheduled for their end of study assessment. Adherence to PA self-monitoring will be indicated by the number of weeks with ≥ 4 days (3 weekdays and 1 weekend day) of valid wear time (≥ 10 hrs). PATH utilization data will be collected via Web analytics, while a post-intervention survey will assess intervention acceptability.

Measures of PA and cardiometabolic outcomes – administered at baseline and 12 weeks (Aim 2). Body weight (assessed via Fitbit Aria 2 digital scale), waist circumference (assessed via Perfect Waist Tape Measure) and blood pressure (assessed via Omron Model BP7450) assessment will be done by the participant using the equipment shipped to their address by the study, and under the supervision of the study team via HIPAA compliant zoom video conference. The instructions for weighing will include asking participants to wear light clothing and stand bare feet on the scale's footpads. The recorded weight will be available to the study team immediately and via Fitbit API. When taking the blood pressure, the participant will be instructed to apply the cuff

on the left bare arm, ensuring that nothing is constraining the arm above the cuff. The easy-wrap ComFit cuff used in Omron Model BP7450 fits standard to large adult arms ranging from 9 to 17 inches in circumference.⁶ After applying the cuff, the participant will be asked to relax, sitting in a chair with both feet resting flat on floor and back straight and supported. After resting for at least 5 minutes with the left arm resting comfortably on a flat surface at heart level, the participants will be asked to turn on the BP machine which will be programmed to take 3 measurements at one-minute interval. Any participant with two readings of elevated BP (>130/80) will be referred to their PCP for management. Blood samples for glycated hemoglobin (HbA1c) and lipids (LDL, HDL, and total cholesterol) will be collected via fingerstick using HemaSpot SE kits which will be mailed to participants ahead of baseline assessment. The samples will be mailed to the lab for analysis using established protocols for dry blood spot method. Type 2 diabetes risk score will be calculated using the ADA risk calculator with covariates that include; age, sex, family history of diabetes, history of hypertension, obesity, and PA.¹⁵ **PA measures:** Barriers to exercise self-efficacy will be assessed via BARSE scale,¹⁶ while ActiGraph GT9X will be used to assess participants' PA patterns including steps, light PA and MVPA. These metrics will be calculated using Freedson adult VM3 cut points.¹⁸ For Aim 2, only the 7- day Actigraph data collected during baseline and 12-wks assessments will be used. Since PATH is expected to increase baseline MVPA by ≥ 60 mins or 6000 steps at the end of the study, percent adherence will be calculated as: [(Post-intervention MVPA - Baseline MVPA) / MVPA goal] $\times 100$ (e.g., [(140-90)/60] $\times 100 = 83\%$ (The same formulae will be used for steps). Pre and post-intervention VO_2 max will be calculated using the non-exercise prediction model for VO_2 peak.² described earlier.

Data/Collection Tool	Baseline	3 months
Screening Questionnaires		
Sociodemographic Questionnaire	X	
Medical History Questionnaire	X	
Physical Activity Readiness Questionnaire	X	
American Diabetes Association Risk calculator	X	X
Barriers Self-efficacy Scale	X	X
Paffenbarger Exercise Habits Questionnaire	X	X
PROMIS SF Sleep Disturbance Questionnaire	X	X
PROMIS SF Sleep-Related Impairment Questionnaire	X	X
Automated Self-Administered 24HR Dietary Recall	X	X
Center for Epidemiologic Studies Depression Scale	X	X
NIH Toolbox Perceived Stress	X	X
Pittsburgh Fatigue Scale	X	X
Physical activity index	X	X
Modified Activity Questionnaire (MAQ)	X	X
Cardiometabolic Assessments		
Zoom supervised self-administered Blood Pressure	X	X
Zoom supervised self-administered Weight	X	X
Zoom supervised self-administered waist circumference	X	X
Height (self-reported)	X	
Glycated hemoglobin (dry blood spot)	X	X
Total cholesterol	X	X
HDL cholesterol	X	X
LDL cholesterol	X	X
Predicted VO_2 peak*	X	X
Accelerometer data on sleep and physical activity	X	X
Randomization via zoom	X	
Intervention Satisfaction Questionnaire		X

Notes: * VO_2 peak for men = $100.27 - (0.296 * \text{age}) - (0.369 * \text{waist circumference}) - (0.155 * \text{resting heart rate}) + (0.226 * \text{PA-index}^*)$; * VO_2 peak for women = $74.74 - (0.247 * \text{age}) - (0.259 * \text{waist circumference}) - (0.114 * \text{resting heart rate}) + (0.198 * \text{PA-index})$

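### Does labelling Beginner content as light activity (<3 METs) undermine a goal and an adherence score expressed in MVPA?

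*Protocol*

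**What the plan says.** The Protocol section on the treatment group sets three content levels by predicted VO₂ max. The lowest group "will be assigned to the Beginner PATH level (includes light intensity PA <3 METs"). The next is the "Intermediate PATH level which includes moderate intensity PA (3-6 METs) in addition to the Beginner PATH content".

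The goal is not split by level: "The goal of the exercise prescription will be to increase baseline MVPA by ≥ 60 min/week or 6000 steps/week". Later in the same section, those who "increase PA by ≥ 10 minutes each week of MVPA or 1000 steps for 6 consecutive weeks will attain the study goal". The coach helps people "progress along the PA continuum (i.e., sedentary to light PA to MVPA"), and participants are "encouraged to select a PA regimen that includes their preferred workout videos and other types of PA appropriate for their fitness".

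Box 1 works the plan through for a Beginner who reports "40 mins of MVPA & 4000 steps derived from walking for 20 mins twice/week" and prefers dance videos. It adds that "Mary can attain the desired volume of weekly PA by either ↑ her routine walks or via her favorite workouts". The sentence just before Box 1 describes her first two weeks as her usual walks plus 10 minutes of dance workouts a week.

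The section on physical activity and cardiometabolic outcomes (Aim 2) lists steps, light activity and MVPA as separate ActiGraph metrics, derived from Freedson adult VM3 cut points. It restates the goal as 60 minutes of MVPA or 6000 steps. It defines percent adherence as MVPA change divided by the MVPA goal, and applies the same formula to steps.

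**The concern.** The Protocol treats light activity and MVPA as different things, both in the progression it describes and in the metrics it records. On its own MET bands, Beginner videos fall below moderate intensity. Box 1 nevertheless seems to count a Beginner's dance minutes toward the weekly MVPA increment: the 10 dance minutes before the box match the 10-minute MVPA step inside it.

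If Beginner videos in fact register as light activity, a participant who follows the prescription mainly through videos could show little or no MVPA gain. Her low percent adherence would then reflect the content she was given rather than her behaviour. In a feasibility study, where adherence informs later work, that would be a misleading signal.

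Moving up a level is not assured either. Participants are asked to work at perceived exertion 12 to 14, while transition is allowed when most workouts are rated 9 or lower.

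**Working it through.** **Reproducing the Protocol's figures**

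- Adherence example (Aim 2 measures): (140 − 90)/60 × 100 = 83.3%, stated as 83%.
- Box 1 end values: 40 + 6 × 10 = 100 min/week, and 4000 + 6 × 1000 = 10,000 steps/week. Both agree with the box.
- Implied step rate: 4000/40 = 1000/10 = 6000/60 = 100 steps/min.

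There is no arithmetic error.

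**How far the score could move**

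Take the Box 1 participant (baseline 40 min MVPA and 4000 steps) and 60 added minutes a week. Let *w* be the added minutes walked, which Box 1 counts as MVPA at 100 steps/min. The other 60 − *w* minutes are Beginner videos. Let *f* be the share of video minutes classed as MVPA and *c* the video step rate. The Protocol gives neither *f* nor *c*, so both are assumed.

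- MVPA score = [*w* + *f*(60 − *w*)]/60
- Step score = [100*w* + *c*(60 − *w*)]/6000

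| Added walking *w* | MVPA, *f* = 0 | MVPA, *f* = 0.5 | MVPA, *f* = 1 | Steps, *c* = 50 | Steps, *c* = 100 |
|---|---|---|---|---|---|
| 0 min | 0/60 = 0% | 30/60 = 50% | 60/60 = 100% | 3000/6000 = 50% | 6000/6000 = 100% |
| 30 min | 30/60 = 50% | 45/60 = 75% | 60/60 = 100% | 4500/6000 = 75% | 6000/6000 = 100% |
| 60 min | 60/60 = 100% | 60/60 = 100% | 60/60 = 100% | 6000/6000 = 100% | 6000/6000 = 100% |

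**What the range means**

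The analyst does not choose *f*. The Aim 2 section classifies each minute by the accelerometer cut points, whatever level or MET label the video carries. For any one participant, the data and the formula give a single MVPA score and a single step score. The table therefore spans possible states of the world, not rival readings of the analysis.

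**Comparing the places that state the goal**

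The treatment-group text, Box 1 and the Aim 2 section all give the same alternatives, MVPA or steps. None says that Beginner videos always count as MVPA, and none says that they never do. Box 1 is consistent if the walks serve the MVPA branch and the videos serve the steps branch.

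The Aim 1 measure of self-monitoring adherence rests on days of valid wear time, so it is untouched.

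**The case for a change.** The strongest contrary case is that the level descriptions are cumulative, so moderate content is what Intermediate adds. Saying that Beginner content includes light activity is then close to saying that it is light activity. With the dance minutes in the example, a reader may fairly conclude that the Protocol expects Beginner videos to produce MVPA while labelling them below it. The steps branch is not a sure rescue: at an assumed 50 steps/min, a video-only participant reaches 50% on steps and, with *f* = 0, 0% on MVPA. Nor does the moderate label on exertion ratings 12 to 14 settle it, because perceived effort can be moderate while the device records light activity.

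Part of this stands. The wording does not say what Beginner videos are expected to contribute, and a low MVPA score in people who stay at that level may partly reflect content. But the extreme result needs several things at once: no added walking, every added minute from videos, every video minute below the cut point, and no change of level by week 12. The Protocol supports none of these as typical, and it expressly allows other activity. A reader who sees both planned scores can recognise the pattern without a new rule. A breakdown by level is a reporting detail that a statistical analysis plan may hold.

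**Conclusion.** No change to the plan follows. Carried out as written, it gives correct MVPA and step scores against a goal that either can meet. The measured quantities do not depend on how Beginner videos are labelled.

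What remains is a point of wording. The level description and the Box 1 example could be reconciled on whether Beginner videos are meant to serve the MVPA branch or only the steps branch. That is for the investigators, and no view is taken here on which is right. In interpretation, the MVPA and step scores should be read together, particularly for participants still at Beginner at week 12.

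The 0% to 100% range for the Box 1 participant rests on assumed values of *f* and on how much of the added time is walked. The 50% to 100% range for steps rests on assumed video step rates of 50 to 100 per minute. The Protocol does not give the share of video minutes classed as MVPA, the video step rate or the proportion of participants at Beginner, so the actual size is unknown.

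### The minimum wear request equals the 10-hour valid-day cut-off, so there is no margin for Aim 1, and a shift in wear hours can pass for a change in activity in Aim 2

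*Protocol*

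**What the plan says.** The wear request is in the Protocol, under Measures of adherence and acceptability (Aim 1): "The PA tracker will be worn on the wrist for at least 10 hours per day when a participant is awake". Wear is meant to be continuous over the trial: "Throughout the 12-week Study, participants will be asked to self-monitor their daily PA".

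The same section defines adherence to self-monitoring as the "number of weeks with ≥ 4 days (3 weekdays and 1 weekend day) of valid wear time (≥ 10 hrs"). The floor of the request and the cut-off for a valid day are therefore the same figure.

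For the end of the study, reminders go out two weeks and one week ahead, asking participants "to wear their PA tracker for 7 days before they are scheduled for their end of study assessment". They state no daily hours, and no matching reminder is described for the baseline week.

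Under Measures of PA and cardiometabolic outcomes (Aim 2), the recordings are restricted: "For Aim 2, only the 7- day Actigraph data collected during baseline and 12-wks assessments will be used". The goal, set in the treatment group section, is to "increase baseline MVPA by ≥ 60 min/week or 6000 steps/week over the course of the study". Percent adherence to that goal has the form "Post-intervention MVPA - Baseline MVPA) / MVPA goal", times 100, and steps are handled in the same way. The formula has no term for wear time.

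**The concern.** A validity cut-off says how little wear an analyst will tolerate. A wear request says what the participant should aim for. Setting both at 10 hours has two consequences.

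First, someone who aims at the stated minimum will fall just short on some days, and those days do not count towards Aim 1.

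Second, a 10-hour day and a 15-hour day satisfy the request equally, yet they capture different shares of the day's activity. PATH relies on workouts that participants fit in at times of their own choosing, so sessions early or late in the day are foreseeable.

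The second consequence matters more. The protocol puts its primary focus on within-group change, so any drift in wear hours between the baseline week and the final week goes straight into the outcome. There are reasons to expect drift. The reminders described concern only the final week, PATH participants see their progress almost as it happens, and the control-group section itself anticipates that tracker use may differ between arms. Activity done with the tracker off cannot be recovered in the analysis.

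**Working it through.** **Inputs from the protocol.** Wear floor 10 h/day; valid day at least 10 h; valid week at least 3 weekdays plus 1 weekend day; 12 weeks; goal 60 min MVPA/week; worked example with baseline 90 and post-intervention 140 min.

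**Assumed inputs (not in the protocol).** Waking day 14 to 16 h; activity spread evenly over the waking day; daily wear normally distributed with mean 10 to 12 h and SD 1 to 2 h; days independent.

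**1. The plan's own figure.** (140 − 90)/60 × 100 = 83.3%. The stated 83% reproduces.

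**2. Share of the waking day not recorded at exactly 10 h of wear**, (W − 10)/W:
- W = 14: 4/14 = 28.6%
- W = 16: 6/16 = 37.5%

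**3. Same 10 h at both visits.** The recorded change is the true change × 10/W. For the protocol's example:
- W = 16: 50 × 10/16 = 31.25 min, and 31.25/60 = 52% instead of 83%
- W = 14: 50 × 10/14 = 35.7 min, and 35.7/60 = 60% instead of 83%

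**4. Wear rises, activity does not.** True MVPA stays at 90 min/week. The apparent change is 90 × (hours added)/W:
- From 10 h to 14 h, W = 16: 90 × 14/16 − 90 × 10/16 = 78.75 − 56.25 = +22.5 min, or 22.5/60 = 37.5% of the goal
- From 10 h to 14 h, W = 14: 90 × 4/14 = +25.7 min, or 43% of the goal
- From 10 h to 12 h, W = 16: 90 × 2/16 = +11.25 min, or 19% of the goal

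A fall in wear gives the same figures with a minus sign. Even spread is a simplification. If the tracker is always on during workouts the loss is smaller, and if a workout is done without it the whole session is lost.

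**5. Margin for the Aim 1 count.** P(valid day) = p = 1 − Φ((10 − mean)/SD). P(valid week) = P(at least 3 of 5 weekdays) × P(at least 1 of 2 weekend days).

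| Mean wear | SD | p | P(valid week) | Weeks of 12 |
|---|---|---|---|---|
| 10 h | 1 or 2 h | 0.50 | 0.50 × 0.75 = 0.375 | 4.5 |
| 11 h | 1 h | 0.841 | 0.945 | 11.3 |
| 11 h | 2 h | 0.691 | 0.747 | 9.0 |
| 12 h | 1 h | 0.977 | 0.999 | 12.0 |
| 12 h | 2 h | 0.841 | 0.945 | 11.3 |

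The Aim 1 count is sensitive only when average wear sits close to the floor.

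**The case against.** The strongest reply is that 10 hours is a floor. The protocol does not cap wear, name particular hours or tell anyone to take the device off. A reader might infer that participants are asked to wear it only for 10 hours and that workouts outside that window are lost by design. The text does not support this: a workout is lost only if the participant removes the tracker and then exercises.

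A reader might also infer that a short day is discarded from the activity outcomes. That is not documented. The 10-hour rule is stated for the Aim 1 adherence count alone. For Aim 2 the protocol gives no valid-day rule, and such handling, like adjustment for wear time, may be in an SAP that is not at hand. Its absence here is no fault.

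For Aim 1, matching the request to the cut-off is coherent, since the measure asks whether people did what they were told. The week rule also has slack: two weekdays and one weekend day may fail. The figure of 4.5 valid weeks in 12 is therefore a worst case and not an expectation.

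Other features of the plan may also lengthen wear. The data collection table lists accelerometer sleep data at both visits, the study team monitors progress through the app, and PATH participants have an incentive to keep the tracker on for workouts.

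All of this narrows the point. What stands is that the request does not ask for the wear that the outcome needs. The features that encourage longer wear do not act equally on the two visits or the two arms, and later adjustment cannot restore activity that was never recorded.

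**Conclusion.** The point holds as a cheap improvement to the wear instruction. No figure in the protocol is wrong.

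For Aim 2, a shift in wear of 2 to 4 h between the two recordings would, with even spread over a 16 h day and a true level of 90 min/week, appear as about 11 to 22.5 min of MVPA change against a goal of 60. Stable wear at the minimum would instead understate a true change, giving 52% to 60% where the plan's example has 83%.

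For Aim 1, week validity is about 0.38 if wear averages exactly 10 h, 0.75 to 0.95 at 11 h and 0.95 to 0.999 at 12 h.

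All these sizes depend on waking and wear hours that the protocol does not give. Only the shared 10-hour figure and the unadjusted difference are established from the text.

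**What to change.** In the Aim 1 measures section:

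- Ask both arms to wear the tracker during all waking hours and during every workout, at minimum in the 7-day baseline and 12-week recordings.
- Give the same instruction and the same reminders before both recordings.
- Keep 10 hours only as the cut-off for a valid day.
- Reconcile the waking-hours wording with the accelerometer sleep data listed in the data collection table, so that the new sentence does not rule out overnight wear where sleep is to be measured.
- Report wear hours by visit and arm beside the activity outcomes, so that a reader can see whether wear shifted.

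The cost is a few changed sentences in the protocol and participant materials, a baseline reminder, and some added burden. The burden falls mainly on those who would otherwise stop at 10 h: for them, 14 to 16 h is 4 to 6 h more, or 40% to 60%. Because burden could itself affect adherence over 12 weeks, limiting the fuller request to the two 7-day recordings is a reasonable compromise. It protects Aim 2 but leaves the Aim 1 margin as it is in the weeks between.

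### Does the wait-list arm's PATH phase lack an assessment schedule, a baseline and a use in Aim 2?

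*Protocol*

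**What the plan says.** The Wait-list control group section of the protocol sets out the crossover: "After 12 weeks, the outcome assessments will be done, and the control group will be given access to the PATH intervention". It continues: "Once given access to PATH, participants will be subject to all the study procedures described for the treatment group". It closes with: "No follow-up is planned after the post-intervention assessments for both the intervention and control groups".

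The section on expected results and pitfalls defends the wait-list design on the ground that "our feasibility study primary focus is on within-group changes".

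The measurement sections are written around two time points. The Aim 1 text says: "Throughout the 12-week Study, participants will be asked to self-monitor their daily PA", and adds that "a post-intervention survey will assess intervention acceptability". The heading of the Aim 2 measures describes them as "administered at baseline and 12 weeks (Aim 2" in its parenthesis, and the text below it states: "For Aim 2, only the 7- day Actigraph data collected during baseline and 12-wks assessments will be used". The same section prints the percent-adherence formula, which is post-intervention MVPA minus baseline MVPA, divided by the goal of 60 minutes.

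The data collection table has two columns, Baseline and 3 months, with no note by arm. Randomization is marked under Baseline only, and the Intervention Satisfaction Questionnaire under 3 months only.

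**The concern.** For a control, the 3-month visit comes before any contact with PATH. If the two columns are fixed calendar visits counted from randomization, three things follow:

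- ActiGraph data from the controls' PATH phase are collected but fall outside Aim 2.
- The satisfaction questionnaire reaches controls before they have anything to rate.
- The adherence formula has no designated baseline for the controls' PATH phase, because week 0 and week 12 both qualify.

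The placement of randomization under Baseline and the description of the study as lasting 12 weeks both seem to favour that reading.

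At stake would be a second set of within-group PATH changes, in a study that calls such changes its primary focus. Acceptability data could be collected too early, and two analysts could score the same control differently.

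**Working it through.** **The protocol's own figure.** The worked example of percent adherence uses a baseline of 90, a post-intervention value of 140 and a goal of 60: (140 − 90)/60 × 100 = 83.3%, which agrees with the stated 83%.

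**How much the choice of baseline could matter.** Suppose a control has 90 min/week at week 0 and 140 after PATH. The week-12 values below are assumed.

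| Baseline used | Calculation | Adherence |
|---|---|---|
| Week 0 (90) | (140 − 90)/60 | 83.3% |
| Week 12, if 100 | (140 − 100)/60 | 66.7% |
| Week 12, if 80 | (140 − 80)/60 | 100% |

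The shift is the change during the wait divided by 60, or 10/60 × 100 = 16.7 points per 10 min/week. It is zero if activity does not change during the wait. The protocol gives no figure for that change.

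**How much precision the controls' PATH phase could add.** Let r be the ratio of control PATH-phase completers to PATH-arm completers. With similar variance in the two arms, pooling narrows a pre/post confidence interval by 1 − 1/√(1 + r): 29% at r = 1.0, 25% at r = 0.8, 21% at r = 0.6 and 0% at r = 0. The protocol text gives no sample size, allocation ratio or dropout, so r is assumed. The formula holds for any wait-list trial. It measures the gain from an optional extra analysis, not the harm from an error.

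**Does the text lead to these outcomes?**

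1. *Schedule.* The crossover text applies every treatment-group procedure to controls once they have PATH, and the next sentence presupposes a post-intervention assessment in both arms. For controls that assessment must come after week 12, at about week 24 if their PATH phase also lasts 12 weeks (an assumption). The table was evidently drawn for one pass through PATH. Randomization under Baseline does not contradict a second pass, since it happens once and would not be repeated.
2. *Pre-PATH value.* The outcome assessments are done after 12 weeks, and access to PATH is then given. That assessment is the last measurement before exposure, as the Baseline visit is for the intervention arm. Week 0, separated from PATH by 12 weeks of booklet and newsletters, is a weak rival.
3. *Satisfaction questionnaire.* Its name refers to the intervention, and the Aim 1 text calls the acceptability survey post-intervention. The treatment-group section describes an end-of-study survey on which resources helped and how PATH could be improved. A control who has not seen PATH could not answer it.
4. *The Aim 2 restriction.* Trackers are worn throughout the 12 weeks. The sentence most plainly says that Aim 2 uses the 7-day assessment windows from that continuous record. Taken literally, it confines Aim 2 to weeks 0 to 12, which is also a legitimate choice.
5. *Consistency of the alleged harms.* The formula and the restriction both stand in the Aim 2 text. If the restriction shuts out the controls' PATH phase, no PATH-phase adherence is scored there and no baseline is in dispute. If that phase is scored, the schedule has been carried over and the data are not shut out. The two harms cannot occur together.

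**The case for a change.** The strongest case for a change is that the protocol never says the schedule restarts. Visit timing, questionnaire timing and the reference value in a printed formula are protocol content. A survey given at the wrong visit cannot be repaired by a later analysis plan. Even with a restart, controls have a 3-month visit before PATH, and no line says that the satisfaction questionnaire is skipped there. The baseline question is also not idle, since the controls' booklet is meant to raise activity.

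Part of this stands: no sentence or column states the repeat, and a short note under the table would be clearer. It does not stand as a defect, because the protocol supplies what is needed to resolve each point: the transfer of procedures, the assessment immediately before access, and the post-intervention label on the survey. Whether post-crossover data also enter a supplementary, non-randomised within-group analysis is commonly settled in a statistical analysis plan. The absence of such an analysis from the protocol is not an error.

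**Conclusion.** No change to the plan follows. The two-column table and the Aim 2 sentence do not spell out the controls' PATH phase, but the crossover text makes a second pass through the same two visits the natural reading, with week 12 as the pre-PATH value and the survey after PATH. Study staff and analysts would be expected to fill the gap that way.

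The randomised comparison at 12 weeks uses data collected before controls receive PATH and is untouched. The within-group focus is already served by the intervention arm's own baseline-to-12-week change. The 16.7-point shift per 10 min/week depends on choosing the less natural baseline and on an unknown change during the wait. The 21% to 29% narrowing depends on assumed completion ratios and describes an optional analysis. Neither is evidence of harm from the text as written.

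This conclusion rests on reading the transfer of all procedures as including the assessments, which the mention of post-intervention assessments in both groups supports.
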